#### **Qualitative Study:**

Saturation is typically considered to occur after 20 interviews, however multiple participant groups are being included in this analysis. The total number of purposely selected participants will therefore be between 23 and 33, as outlined in the group descriptions in section [3.2](#). If data saturation is felt to have occurred, participants will only be interviewed if the minimum group size has not been met. If a participant withdraws and the minimum number for any group falls below the sample sizes described in section 3.2, participants will be replaced. If, however, the minimum numbers are maintained the participant will not be replaced.

### 6.2 SAMPLING

#### **Cross-sectional study:**

Date and Version No: 04/11/2024; Version 1.3

Trainee collaboratives are a well-proven data collection method which limits the patient burden and encourages broad participation, as well as ensures that only the direct care team accesses identifiable information. A trainee collaborative model will be used, with a Lead Trainee or Associate PI† and a Principal Investigator or Co-Investigator responsible for data collection in each unit ([see section 9](#)).

Local clinicians will identify patients from elective and emergency general surgical operating lists occurring during the study period. All patients undergoing cholecystectomy during the study period should be screened for inclusion by any clinical team member.

Data will be prospectively collated in a Microsoft Excel Spreadsheet, and de-identified information will be entered directly into REDCap at each study site. A minimum dataset cross-referencing a study ID and patient identifiers will be kept locally. The local investigators will be responsible for ensuring that the spreadsheet is kept and maintained according to local data security guidelines, and, as a bare minimum, the spreadsheet should be held on a secure, institution-approved drive location and password protected. Patient identifiers held locally will be excluded from transfer to the main trust undertaking analysis, and sites will be encouraged to keep a secure cross-referencing database so that patients can be locally identified for internal validation or obtaining missing data. Data will be submitted to the primary investigating team centrally at UHP using REDCap to facilitate secure transfer and assess the dataset's completeness. Individual surgeons will not be centrally identified and will strictly remain anonymous.

### **Qualitative study:**

Participants will be selected from patient lists at study sites, from public support groups, from within the NHS and through specialty association mailing lists. [Each group](#) will consist of participants who have been purposively selected to represent a cross-section of the relevant population.

As a contingency, in the event of either an un-representative mixture of participants, or the minimum number for any group not being achieved, convenience sampling will be used to identify and recruit participants from the relevant staff and patient groups at UHP. If required, snowballing will be used to aid recruitment.

---

† This definition is dependent on whether the study is adopted by the NIHR and accepted to the Associate Principal Investigator scheme.

Date and Version No: 04/11/2024; Version 1.3

## 6.3 ANALYSIS OF ENDPOINTS

### Cross-sectional Study

#### a. Internal pilot analysis

Descriptive statistics (including means, standard deviations, medians, inter-quartile ranges and ranges, as appropriate for continuous variables and frequency and percentage for categorical variables) will be summarised for all demographics and potential predictive factors of iGBC collected.

The prevalence of iGBC and BHC will be presented as a percentage with confidence intervals.

The number of patients undergoing cholecystectomy, the number of patients eligible, the number of patients (and percentage) recruited, and the number of patients (and percentage) undergoing the procedure will be summarised overall and by site.

The level of data completeness (demographics, potential risk factors and outcomes) will be summarised by frequency and percentages overall and by site.

Descriptive statistics will be used for

- rates of iGBC and BHC in the pilot population
- rates of recruitment of patients to the study
- data completeness

The dataset will be evaluated to identify commonly incomplete data points (core data points for which completeness is <80%). Units and collaborators will then be surveyed to evaluate the challenges associated with these areas. Following the result of this survey, the study team will discuss each incomplete data point and make suitable adjustments to the power calculation and data points for collection according to the figure below.

Date and Version No: 04/11/2024; Version 1.3

	Variable with large effect size or significance for iGBC in pilot, or in previous studies	Variable with low or uncertain effect size or significance for iGBC
Completeness likely to improve to >80% following intervention (e.g. change in the phrasing of a question or definition, change to patient record sheet)	Retain data point for full study	Retain data point for full study
Completeness unlikely to improve following intervention	Retain data point for full study, consider adjusting power calculations to accommodate level of completeness achieved in pilot	Consider whether omitting data point from full study is justified

Rates of recruitment will be considered in the context of the power calculation and the time initially allocated to complete data collection. Where necessary, proposed timeframes will be adjusted in the context of the power calculation and with details of potential participating units, prior to data collection for the full study beginning.

Feasibility of the study may be hypothetically established, however adequate funding and sufficient participating centres with at least firm expressions of interest are required for actual progression. A final analysis and assessment against the following criteria (see table) will inform whether it is considered practically feasible to progress and therefore seek funding to continue the study.

Date and Version No: 04/11/2024; Version 1.3

	Green (Progress to full trial)	Amber (May progress, subject to revision and review)	Red (Not to progress without further evaluation and/or development)
Variables	Sufficient variables completed >80% for meaningful diagnostic score development	Insufficient variables completed >80% for meaningful diagnostic score development, likely to resolve with adaptations (e.g. changes to CRF)	Insufficient variables completed >80% for meaningful diagnostic score development, and unlikely to improve with adaptations
Centres  *Time to meet recruitment target based on mean per-centre recruitment rate in fP-iGBC.	Sufficient centres to meet recruitment target* within two years	Sufficient centres to meet recruitment target* within three years (aim to recruit centres to shorten data collection period)	Insufficient centres to meet recruitment target* within three years.

#### b. Full prospective study analysis

A summary of the demographics, potential predictive factors and outcomes will be presented.

A multivariable predictive model will be developed using potential risk factors available before the decision to send cholecystectomy specimens for RHA to identify patients with iGBC. The predictive model will be in the form of a logistic regression model and, therefore, will be interpreted using odds ratios. A post-estimation method to reduce the possibility of overfitting will be implemented.

Internal validation of the predictive model will be performed using a method of resampling from the original data (e.g. cross-validation or bootstrapping). Measures of model performance, including discrimination, calibration statistics and clinical usefulness (e.g. net benefit), will be presented.

Date and Version No: 04/11/2024; Version 1.3

A complete, detailed statistical analysis plan (SAP) for each of the pilot and the complete study will be available at a later date.

**Qualitative Study:**

[figure not shown]
Thematic analysis of interview transcripts will be performed using dedicated qualitative analysis software and data-driven to reduce the potential for interviewer bias. The analysis will start after the first 3-4 interviews to inform subsequent interviews and actively assess data saturation. Where appropriate, the interview guide may be adjusted to maximise the richness of the data. Data extracts will be coded and categorised into themes, following proper guidance. Coded data will be reviewed and agreed upon by at least two researchers. A provisional summary will be sent to 3 patient participants and to 3 professional participants, for member checking. Outcomes of interest will be aligned with the aims of the qualitative study as defined previously.

## **7. DATA MANAGEMENT AND DATA SHARING PLAN**

To comply with the Data Protection legislation, information will be collected and used fairly, stored safely and not disclosed to any unauthorised person. This applies to both manual and electronically held data.

The Chief Investigator will preserve the confidentiality of participants taking part in the study and ensure the EU General Data Protection Regulation (GDPR), in conjunction with the UK Data Protection Act 2018, which sets out the statutory requirements for processing personal data, is adhered to.

## 7.1 DATA FLOW DIAGRAM

Date and Version No: 04/11/2024; Version 1.3

## 7.2 DESCRIPTION OF THE DATA

The following discrete data points will be collected. Data points will be re-evaluated following the pilot, and the feasibility of collection of each data point will be considered.

A summary of these data points is presented in the table below, and a fully exploded list of variables is available in the appendices. Not all data points will be applicable to all patients, for example where variation in practice exists. These dependent data points, and their sub-points are marked with an asterisk (\*).

Core data points (all patients)	Study ID Patient Factors Referral Pathway Indication for Surgery Laboratory findings Intra-operative Findings Histology
Semi-dependent data points (minimum dataset required per patient)	Imaging findings (minimum one modality, include all directly relevant to patient's cholecystectomy pathway).
Dependent data points (applicable patients) *	Pre-operative interventions Intra-operative imaging Progression to CBD exploration

## 7.3 COLLECTION OF DATA AND STUDY MATERIALS

### Cross-sectional Study:

Trainee collaboratives are a well-proven data collection method that limits the patient burden and encourages wide participation. A trainee collaborative model will be used, with a Lead Trainee or Associate Principal Investigator (PI)‡ responsible for data collection in each unit under the supervision of a formal PI. Each unit will be asked to recruit as many patients as possible, and will be provisionally asked to target a minimum of 10 recruited patients per month of inclusion.

---

‡ This definition is dependent on whether the study is adopted by the NIHR and accepted to the Associate Principal Investigator scheme.

Date and Version No: 04/11/2024; Version 1.3

Data will be prospectively collected on a digital Case Report Form (CRF), and may either be initially collated in a Microsoft Excel Spreadsheet, or entered directly onto REDCap at each study site. A separate, minimum dataset cross-referencing a study ID and patient identifiers must be kept locally to allow data validation and identification and/or recovery of missing variables. The local investigators will be responsible for ensuring that the spreadsheet is kept and maintained according to local data security guidelines, and, as a bare minimum, the spreadsheet should be held on a secure, institution-approved drive location and password protected. Only de-identified information will be exported to the central team at UHP using REDCap. This tool facilitates secure data transfer, can help to ensure de-identification and has the facility to assess the dataset's completeness. Individual surgeons will not be centrally identified and will strictly remain anonymous.

In order to ensure the integrity of the data, the dataset will be subject to a regular review process during data collection periods to identify outliers, which may be the result of typographic errors. This will allow timely feedback to the collaborating researchers and ensure that the final datasets are of high quality.

To further validate the dataset, units will be asked to perform an internal validation exercise. As outlined in section 9, this will be conducted in each participating unit by a collaborator who is not otherwise involved in data collection and will act independently from the other collaborators at the site. For the feasibility phase, 10% of patients will undergo this exercise. For a unit achieving the provisional target of 10 patients each month, this will equate to six records. The data validator will be asked to review the clinical record of the recruited patient and re-enter data from several core data points on a new CRF. This duplication of data entry will allow an assessment of concordance and give an idea of the quality of the dataset. The need for ongoing internal validation, and the proportion of patients required to validate the dataset will be reviewed following the feasibility phase.

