## **4.4 STUDY ASSESSMENTS/ INTERVENTIONS**

### **Cross-sectional study:**

No deviation from routine patient care is required. The cross-sectional study will collect baseline information about the patient's background, including age, ethnicity, co-morbidity, BMI, pre-operative investigations and intra-operative findings, which will largely be available from the patient's written and digital records. The diagnosis/diagnoses of the postoperative histopathology report will be collected once available and is considered a result from the event of interest (the cholecystectomy).

Consequently, there is no longitudinal follow-up required.

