#### *Collaborators – Data Collection*

Lead Trainees and PIs are required to recruit sufficient (trainee) collaborators to monitor operating lists and to identify, recruit and collect data from patients for each component of the study. Collaborators include the Lead Trainee and PI, and can be recruited from any grade of doctor or the allied health professions, including Physician Associates, Nurses etc, however must:

1. Be drawn from members of the direct care team for patients undergoing cholecystectomy.
2. Ordinarily have access to review necessary results.
3. Have sufficient training and/or experience to provide the knowledge and understanding of common terminology found in reports and letters, which may need to be interpreted before input to the data collection tool.
4. Meet any generic organisational requirements for involvement in research within the participating organisation.

There is no centrally defined maximum number of collaborators per organisation, as in common with Lead Trainees it is recognised that many collaborators will be rotational, and that organisations will vary in their surgical volumes. However, to be considered for authorship each collaborator should be able to identify and collect data from 2 patients each month. For example, in a unit meeting the initial feasibility target of 10 cholecystectomies each month, 5 local collaborators (including the PI and Lead Trainee) would be suggested as an appropriate maximum. Data collectors should remain actively involved with the study for a minimum of one rotation (but not less than four months, as applicable to their job role, unless data collection starts or finishes mid-rotation), or one year for permanent staff. Collaborators are not required to remain involved outside of data collection periods.

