#### *Collaborators – Limited role*

Where it may assist local teams to utilise other members of the direct care team to identify and screen patients, or to permit “live” operative data entry by the performing team, a limited access role will be available in REDCap in order for accurate, prospective recording of intraoperative events. These collaborators will be able to access the screening and operative findings sections of the eCRF. The Lead Trainee and PI are responsible for determining whether their contribution is sufficient to qualify for authorship, through comparison to those collaborators undertaking data collection and validation.

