**APPENDIX 1 – SCHEDULE OF EVENTS**
**Quantitative Component**

Procedures	- 2 weeks	Start of recruitment period	Operating List Planned	Day of operation	End of recruitment period	Histology	+ 8 weeks
Public Announcements	X	X	X	X	X		
PIS available online + paper	X	X	X	X	X		
Start of data collection		X					
Demographics, Imaging, Bloods			X	X			
Intra-operative findings				X			
Histology						X	
Monthly local performance updates		X	X	X			
Fortnightly data upload reminders					X		
Data upload ended (locked)							X

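### Subjective predictors may be recovered or interpreted after the histology report is known, with no rule on entry order, late-entry flagging or blinding

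*Protocol*

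**What the plan says.** Section 7.3 describes collection as prospective but allows an intermediate step: "Data will be prospectively collected on a digital Case Report Form (CRF), and may either be initially collated in a Microsoft Excel Spreadsheet". The local cross-reference file "must be kept locally to allow data validation and identification and/or recovery of missing variables", and section 6.2 gives it the same purpose, "so that patients can be locally identified for internal validation or obtaining missing data". Neither section limits recovery in time or by type of variable.

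Section 4.4 says where predictors come from: "pre-operative investigations and intra-operative findings, which will largely be available from" the patient's written and digital records. Section 9.1 requires data collectors to have routine access to the results they need and to understand "common terminology found in reports and letters, which may need to be interpreted before input to the data collection tool". For theatre data, section 9.1 says "a limited access role will be available in REDCap in order for accurate, prospective recording of intraoperative events", but this is offered where it helps the local team and is not required.

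Appendix 1 places demographics, imaging and bloods at list planning or the day of operation, intra-operative findings on the day of operation, and histology later. Monthly performance updates run during recruitment. "Fortnightly data upload reminders" are marked at the end of recruitment, and the single lock is in the plus 8 weeks column. Section 4.3 ends data collection six to eight weeks after recruitment closes in each unit.

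Section 6.3b restricts the model to risk factors that were available before the decision to send the specimen.

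**The concern.** A score meant to decide which gallbladders go to histology must be built on predictors recorded without influence from the histology. If a collector completes or re-reads the record of a patient already known to have cancer, two things can happen in cases but not in the other patients. The notes may be searched harder, so that features left unrecorded elsewhere are found. Equivocal wording on wall thickness, inflammation or appearance may also be read as positive. Both would tend to inflate odds ratios for factors believed to raise risk, and to make the score look better than it would be when used before any histology exists. Section 1.1 names macroscopic cholecystitis and a thick-walled gallbladder among the recognised risk factors, so items of this kind are plausible candidate predictors.

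The planned checks would not reveal the problem. Cross-validation or bootstrapping (6.3b) resamples the same recorded values. The validator in 7.3 is independent of the other collectors but re-enters data from the clinical record, with no blinding to histology stated. Two readers who both know the result can agree and share the bias. The outlier review in 7.3 is aimed at typing errors.

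**Working it through.** **1. What the protocol fixes about timing.**
- Planned order: predictors at or before operation, histology afterwards (Appendix 1).
- Enforcement of that order: none stated. Live theatre entry is optional (9.1), and a spreadsheet may come before REDCap (7.3), so a REDCap time stamp need not show when a value was first recorded.
- Open window: in a pilot unit recruiting for six months (6.1), the record of a patient operated on at the start stays open for about six months plus six to eight weeks (4.3).
- Who enters: direct-care staff with results access (9.1). Intra-operative findings and histology are both core data points (7.2), and no separation of who enters them is described.

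**2. Number of cases.** Section 6.1 assumes 0.2% prevalence, Nagelkerke R² of 0.3 and 20 parameters. It states no shrinkage factor; I assume S = 0.9.
- Maximum Cox–Snell R² = 1 − exp(2[0.002 ln 0.002 + 0.998 ln 0.998]) = 0.02844
- R² = 0.3 × 0.02844 = 0.00853
- n = 20 / [(0.9 − 1) × ln(1 − 0.00853/0.9)] = 20,995.3, which reproduces the stated 20,996
- 20,996 / 0.8 = 26,245, as stated

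Expected cases: 20,996 × 0.002 = 42; 26,245 × 0.002 = 52; 30,000 × 0.002 = 60; pilot, 500 × 0.002 = 1.

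**3. Illustration A: re-interpretation (assumed values).** Take a factor unrelated to cancer, present in 10% of patients. The odds in non-cases are 0.1/0.9 = 1/9. With 42 cases, 4.2 are truly exposed. If k further cases are recoded as present, OR = 9 × (4.2 + k)/(37.8 − k).

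| k | 42 cases | 60 cases: 9 × (6 + k)/(54 − k) |
|---|---|---|
| 2 | 9 × 6.2/35.8 = 1.56 | 9 × 8/52 = 1.38 |
| 4 | 9 × 8.2/33.8 = 2.18 | 9 × 10/50 = 1.80 |
| 6 | 9 × 10.2/31.8 = 2.89 | 9 × 12/48 = 2.25 |

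At 20% prevalence, re-reading 5% to 20% of truly negative cases (about 2 to 7 of 42) gives 1.26 to 2.25.

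**4. Illustration B: truthful but selective recovery (assumed values).** Take a null factor with 20% true prevalence, where 20% of positives are left unrecorded and read as absent, and these are recovered only in cancer cases. Recorded prevalence is 20% in cases and 16% in non-cases. OR = (0.20/0.80)/(0.16/0.84) = 1.31. With 10% to 30% unrecorded, the range is 1.14 to 1.54.

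**The case against.** A reader might infer that any predictor entered after the report breaches section 6.3b. The protocol does not support that. Section 6.3b concerns when the information existed, not when it was typed. An operative note, blood result or scan report written before histology and transcribed later still qualifies.

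Nor does the protocol defer entry to the end of recruitment. Appendix 1 schedules predictors at or before operation, with monthly updates, and 7.3 adds regular data review with prompt feedback. Section 9.1 says only that terminology in reports and letters "which may need to be interpreted before input to the data collection tool". It is a competence requirement and does not mention operative notes. Age, BMI and bloods leave little to interpret.

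The illustrations assume a null factor and errors confined to cancers, and nothing in the protocol shows that this will occur. Finding a feature that was truly present is not a false record. The CRF, the data flow diagram and the variable list were not available to this review. Sections 4.3 and 9.1 show that the eCRF already uses gating and section-level access, so an entry order may exist in the build.

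Most of this stands, and it narrows the point to subjective items. It does not remove it. Illustration B shows that truthful recovery still biases an odds ratio when it is selective. No rule stated in the protocol prevents either mechanism. The analysis could be left to the SAP, but the flag it needs must be created when the data are entered.

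**Conclusion.** The point holds in a limited form. The protocol plans the right order but does not secure it for subjective predictors, mainly intra-operative findings. It permits local recovery up to a lock that follows histology, by staff who can see results, with no flag and no blinding. Late transcription of fixed values is not a fault.

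The size of any bias cannot be derived from the protocol. With 42 to 60 expected cases, a handful of entries would matter: 2 to 6 recoded cases on a null factor of 10% prevalence give odds ratios of 1.6 to 2.9 with 42 cases and 1.4 to 2.3 with 60. These rest on assumed counts and show sensitivity, not a forecast. This is a cheap improvement, best made before the full study. The pilot expects about one case and is followed by a pause of 18 to 24 months (4.1), so nearly all cases are still to come.

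**What to change.** In section 7.3 and the eCRF:
- Require the pre-operative and intra-operative forms to be completed before the histology form opens.
- Record the date on which each predictor was first recorded, including in any local spreadsheet.
- Allow later recovery or change only with an audit flag and, where possible, by someone unaware of the histology.

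In section 6.3b or the SAP, keep flagged values in the main analysis and report a sensitivity analysis for subjective predictors that treats flagged post-histology entries as missing.

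The cost is a form-order rule, a date field, a flag and one extra analysis. Apparent completeness may fall slightly. The sensitivity analysis will be less precise because cases are few, which is why the flagged values stay in the main analysis. Form order reduces knowledge of the result at entry but cannot guarantee blinding, since collectors have results access and may use a spreadsheet first.

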## 6. STATISTICS

### 6.1 THE NUMBER OF PARTICIPANTS

#### **Cross-sectional study:**

The required power to develop a diagnostic score for iGBC, assuming a 0.2% prevalence, Nagelkerke's  $R^2$  of 0.3 and 20 diagnostic parameters, is 20,996. Allowing for a 20% rate of incomplete data, 26,245 participants would be required. It is possible that, following the feasibility study, it will be clear that more than 20 diagnostic parameters are required. The study will, therefore, aim to recruit up to 30,000 participants to ensure adequate power.

An internal pilot study will be undertaken between 8 participating units to ensure the feasibility of recruiting so many participants and calibrating the final recruitment target. Data collection will be paused at the first of 500 participants between all participating units or six months of completed data collection in each participating unit, allowing for the internal pilot to be evaluated. For a sample size of 500, an iGBC incidence of 0.2% will be estimated with a margin of error of +/- 0.39%. Rates of recruitment, completeness of data, and events will be evaluated. The assumptions above will be adjusted, and the corrected data will be used to re-calculate the final recruitment target before data collection for the complete cross-sectional study begins.

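### The feasibility-phase re-entry check does not name histology or target recorded cancers, so its concordance figure can say almost nothing about the accuracy of the rare endpoint

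*Protocol*

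**What the plan says.** Protocol section 7.3 (cross-sectional study) asks each unit to run an internal validation exercise through a collaborator who takes no other part in data collection. Its size is set for the pilot only: "For the feasibility phase, 10% of patients will undergo this exercise". The protocol works this through for one site: "For a unit achieving the provisional target of 10 patients each month, this will equate to six records". The validator goes back to the clinical record and is to "re-enter data from several core data points on a new CRF". Which core data points are meant is not said, nor how the 10% is chosen. Section 7.2 lists histology among the core data points, so it may be one of those re-entered, but no text says that it is.

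For the full study the question is open: "The need for ongoing internal validation, and the proportion of patients required to validate the dataset will be reviewed following the feasibility phase".

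Section 7.3 describes one other data check: "the dataset will be subject to a regular review process during data collection periods to identify outliers". Its stated concern is unusual values that may be typing errors.

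The outcome comes from the postoperative histopathology report (section 4.4). Section 9.1 requires data collectors to be trained or experienced enough to understand "common terminology found in reports and letters, which may need to be interpreted before input to the data collection tool".

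On incidence, section 6.1 assumes 0.2%, and states for the pilot: "For a sample size of 500, an iGBC incidence of 0.2% will be estimated", with a margin of 0.39 percentage points either way. Section 1.1 gives a UK range of 0.14% to 0.3% for iGBC and about 2% for iGBC and BHC together.

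**The concern.** A flat percentage of records suits common variables such as age, bilirubin or wall thickness, because 50 re-entered records then give 50 informative comparisons. It does not suit an outcome that occurs once in 500 records. Almost every re-entered record will be an unremarkable gallbladder on which both readers agree. A high concordance figure would be reported, and it would carry almost no information on whether recorded cancers are cancers, or on how dysplasia and xanthogranulomatous cholecystitis are separated from cancer at data entry. If histology is not among the chosen fields, it would carry none.

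The outlier review does not fill the gap as described. A wrong but permitted histology category is not an unusual value, and no comparison with the report is stated.

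Two uses of the pilot are affected. Section 6.1 has the pilot's events evaluated and its assumptions updated before the recruitment target is recalculated. Section 7.3 has the need for validation, and its proportion, decided after the pilot. That second decision would draw on an exercise with next to nothing to say about the endpoint.

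**Working it through.** **Inputs.** Re-entry share 10% and 10 patients per unit per month (section 7.3). Six months, 8 units, pilot maximum 500, prevalence 0.2%, 20,996 evaluable, 26,245 after allowance for incomplete data, ceiling 30,000 (section 6.1). iGBC 0.14% to 0.3%, and iGBC plus BHC about 2% (section 1.1). Pilot range 300 to 500 (study summary).

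**The protocol's own figures reproduce.**
- Records per unit: 10 × 6 × 0.10 = 6. Eight units at target give 480 patients and 48 re-entered records; the maximum of 500 gives 50.
- Pilot margin: 1.96 × √(0.002 × 0.998 / 500) = 0.39%.
- Allowance for incomplete data: 20,996 / 0.8 = 26,245.

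**Chance that the pilot exercise re-checks any cancer.** Assume the sample is drawn without regard to outcome, which the protocol does not state. With m re-entered records and incidence p, the expected number of cancers is m × p and the chance of at least one is 1 − (1 − p)^m.

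| Pilot N | m | p | Expected cancers re-checked | Chance of at least one |
|---|---|---|---|---|
| 500 | 50 | 0.14% | 0.07 | 6.8% |
| 500 | 50 | 0.2% | 0.10 | 9.5% |
| 500 | 50 | 0.3% | 0.15 | 14.0% |
| 480 | 48 | 0.2% | 0.096 | 9.2% |
| 300 | 30 | 0.2% | 0.06 | 5.8% |

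Within one unit's six records the chance is 1 − 0.998^6 = 1.2%. For BHC alone, at 2% − 0.2% = 1.8%, about 50 × 0.018 = 0.9 of 9 cases would be re-checked.

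**What a clean result would show.** If histology were re-entered in all 50 records with no discordance, the one-sided 95% upper limit on the error rate is 1 − 0.05^(1/50) = 5.8%. That is about 29 times the assumed incidence (5.8 / 0.2).

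**Full study, only if 10% were kept.** At N = 26,245 about 2,624 records are re-entered and 26,245 × 0.002 = 52.5 cancers are expected. Of these, 5.2 would be re-checked, with a 99.5% chance of at least one. About 90% would not be re-checked.

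**Illustration of miscoding.** The protocol gives no error rate, so these rates are assumptions. If a fraction e of non-cancer records is coded iGBC and no cancer is missed, the apparent rate is 0.002 + 0.998e, and the false share of recorded cancers is 0.998e / (0.002 + 0.998e).

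| Assumed e | Apparent rate | False share | Share of BHC reports miscoded, if all errors arise there (0.998e / 0.018) |
|---|---|---|---|
| 0.05% | 0.25% | 20% | 2.8% |
| 0.1% | 0.30% | 33% | 5.5% |
| 0.2% | 0.40% | 50% | 11% |

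The last column shows what these rates would require if errors came only from BHC reports. The documents do not say whether that is realistic.

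**The case against.** The strongest reply is that the 10% is expressly a feasibility-phase figure. The pilot analysis is descriptive (section 6.3a). The score is built in the full study (section 6.3b), for which a trials unit is to be brought in (section 9) and for which the amount of validation is still to be decided. The pilot contributes at most 500 of 26,245 records (1.9%) and about one cancer. A reader might infer that miscoded histology will enter the score unnoticed. The documents do not support that, because they fix no validation proportion for the data that build the score and give no miscoding rate.

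A reader might also infer that cancers will almost never be re-checked. That fits the pilot only. Even if 10% were kept, about five would be re-checked in the full study, and the fair criticism there is that about 90% would not.

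Nor is re-entry the only check of any kind. There is the central outlier review, supervision by a principal investigator (section 7.3) and sponsor monitoring (section 8.5). None is described as comparing histology with the report, so re-entry remains the only stated comparison with source. The section 9.1 wording on interpreting reports is a competence requirement, a safeguard rather than evidence of poor coding.

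Finally, sampling error dominates the pilot rate. The stated margin of 0.39% on 500 is about two cases either way, whereas 0.05% to 0.1% miscoding adds 0.25 to 0.5 of a case. Verifying one cancer will not make that estimate precise, and the tabulated progression criteria (section 6.3a) do not use it.

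These points stand and limit the finding. They do not answer the narrower one: the exercise, as specified, cannot inform endpoint accuracy, and the deferred decision is to follow from it. Later repair is also harder, since upload closes eight weeks after recruitment ends (Appendix 1) and collaborators need not stay involved between collection periods (section 9.1).

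**Conclusion.** The point holds for the feasibility phase, as a design weakness that is cheap to remove. No figure in the protocol is wrong. Section 7.3 names neither histology as a re-entered field nor recorded iGBC and BHC as records to verify. With sampling blind to outcome, the pilot exercise has about a 1-in-10 chance of touching any cancer (9.5%; 6.8% to 14.0% over the stated incidence range at N = 500). Its concordance result therefore cannot bear on the rare endpoint or guide the later choice of validation effort.

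The result rests on two assumptions: that the 10% is not selected by outcome, and that the stated incidence applies. For the full study it is conditional on 10% being kept. No size can be given for any bias in the incidence or the score, because that depends on an unknown coding error rate.

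**What to change.** Amend section 7.3 as follows.

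1. Name the histology diagnosis as a field that is re-entered in every validated record.
2. In the pilot, have the existing independent validator re-extract histology for every record coded iGBC or BHC, plus a random 10% of the remaining records.
3. Resolve discordances against the pathology report before data lock.
4. In the full study, verify every record coded iGBC, whatever proportion is chosen for the rest.

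**Cost.** In the pilot about 500 × 0.02 = 10 coded records plus 10% of the other 490 (49), so 59 in place of 50: about 9 extra across 8 units. In the full study, 52 coded iGBC records at N = 26,245 and 60 at N = 30,000, of which about 5 or 6 would be covered anyway if 10% were kept. The validators (section 9.1) and the local key linking study ID to patient (section 7.3) are already planned. Concordance must then be reported by outcome stratum, because a pooled figure would be distorted by the oversampled positives.

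**Limit.** The random sample of records coded negative is what could reveal missed cancers. At about 49 records in the pilot it remains a coarse check, and the report should say so.
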